6.2 Study setting

The study setting is the Bwaila STI Clinic (BSC) and Bwaila VMMC clinic at Bwaila District Hospital (BDH). BDH is a public secondary level facility in Lilongwe and the only facility offering specialized STI care situated in a busy central town area of the Lilongwe district. Approximately 80 patients visit BSC per day. The VMMC clinic and BSC are about 300 meters apart within the BDH campus. Twenty (20) people comprising nurses, clinicians, HIV testing services (HTS) counsellors, receptionists and support staff run BSC. As standard of care, all STI patients at BSC receive group health education (GHE) and are offered opt-out provider initiated HIV testing as standard of care, before receiving care for their STIs. We propose to integrate intensified health education to the GHE. About two to three GHE sessions are conducted per day with different cohorts of patients based on their time of arrival at the clinic however only one GHE includes education on VMMC. The clinic receptionist assisted by a nurse or counsellor conducts GHE. The first GHE session includes a mobilizer from the VMMC clinic who conducts an educational talk on VMMC every morning at the STI clinic and refers men to the VMMC clinic using referral slips. The additional GHE sessions do not have educational talks by the mobilizer. We will train the clinic receptionist, counselors, nurses and the mobilizer to conduct intensified health education. As standard of care, uncircumcised men with STIs are supposed to be offered VMMC at the STI clinic by clinicians however this is not reinforced. Data on demographics, HIV testing and treatment, sexual history and STIs are collected routinely through an electronic medical registry.

The VMMC clinic has a director, administrator, program officers, clinicians (male and female), nurses (both male and female), data clerks, mobilizers and support staff. A team consisting of one clinician, an assisting nurse and other support staff conduct circumcisions. Circumcisions are

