6.3 Sample Size Calculation and Justification

Data on the incidence of VMMC among men with STIs is unavailable. Based on routine data, the Bwaila STI clinic sees about 60 patients per day. Of these, 27 patients are men. Using the prevalence of circumcision from the MoH integrated HIV Program third quarter report of 28% among men with STI, we estimate that at least 19 uncircumcised men will visit the STI clinic per day and at least 380 uncircumcised men per month. Since the project implementation period is expected to be about 6 months, we expect that a minimum of 2280 uncircumcised men will be exposed to our intervention and observed for VMMC uptake.

We will offer all men who express interest in VMMC to participate in a survey. We anticipate between 5-15% of the men will decline participation in the survey. All (approximately 12) healthcare workers will be offered to take the surveys. All available experts (approximately 10) will be offered to take a survey.

Sample size for surveys

Based on the total sample size of 80 men indicated below, we calculated that 67 surveys are required for each intervention component to achieve 95% confidence level with 5% margin of error [38]. We will offer all men who express interest in VMMC to participate in a survey. We anticipate between 5-15% of the men will decline participation in the survey. All (approximately

12) healthcare workers will be offered to take the surveys. All available experts (approximately 10) will be offered to take a survey.

Data Analysis

Overall, we will use descriptive statistics such as mean, median and proportion to describe the demographic characteristics of the study population by implementation block. Demographic characteristics will include but not limited to age, marital status, educational status and socio-economic status. These characteristics will be compared with the SOC group using Student's T-test or Chi-squared test at $\alpha=0.05$ and 95% confidence interval, assuming normal distribution.

Objective 1: To compare uptake of voluntary medical male circumcision between the standard of care and the different combinations of the RITE intervention among men attending Bwaila STI clinic in Lilongwe Malawi

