Uptake will be calculated as a proportion - the number of men who will undergo VMMC divided by the number of uncircumcised men offered VMMC at the STI clinic. Uptake will be calculated for each implementation block. Uptake for each block will be compared against SOC using Student's T-test at $\alpha=0.05$ significance level and 95% confidence interval, assuming normal distribution.

Objective 1a: To compare time-to-uptake of voluntary medical male circumcision between the standard of care and intervention period among men attending Bwaila STI clinic in Lilongwe Malawi

Time-to-uptake of VMMC will be calculated as the number of days taken for an individual to undergo circumcision at the VMMC clinic from the day they were offered circumcision at the STI clinic. To compare time-to-uptake between SOC and the intervention blocks, we will conduct time-to-event analysis to estimate duration to circumcision and Kaplan Meier curves will be plotted and compared between SOC and implementation blocks. We will also study factors affecting time-to-uptake using cox regression.

Objective 1b: To assess factors affecting uptake of voluntary medical male circumcision among men attending Bwaila STI clinic in Lilongwe Malawi

We will assess factors affecting uptake of VMMC using logistic regression modeling. We will use univariate models to assess association. Covariates with $P<0.05$ and those based on expert knowledge of this topic will be fit into multivariate logistic regression models to control for confounders.

Objective 2: To develop STI clinic setting-specific voluntary medical male circumcision educational material at Bwaila STI clinic in Lilongwe Malawi

We will use thematic analysis approach for qualitative analysis of the consultative meeting notes. The notes will be coded and salient themes will be identified. The content and delivery methods will be deduced from the salient themes.

Objective 3: To assess the acceptability, appropriateness and feasibility of the adaptable RITE intervention among men and healthcare workers at Bwaila STI clinic in Lilongwe, Malawi.

We will use mixed methods to assess acceptability, appropriateness and feasibility. For acceptability, appropriateness and feasibility quantitative surveys, these outcomes will be

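### Student's t-test on yes/no uptake gives a 95% interval of the wrong width when both the denominators and the uptake variances differ between standard of care and a block

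*Combined protocol and SAP*

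**What the plan says.** Section 6.3 (Sample Size Calculation and Justification), under Data Analysis, Objective 1, defines the outcome: "Uptake will be calculated as a proportion - the number of men who will undergo VMMC". The denominator is every uncircumcised man to whom the STI clinic made an offer of VMMC. The section then sets the comparison: "Uptake for each block will be compared against SOC using Student's T-test". Alpha is 0.05, and a 95% interval is to be given under an assumption of normality.

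No other text changes this. Chi-squared is offered for demographic characteristics, a test of proportions for the surveys under Objective 3, and logistic regression for the factors affecting uptake under Objective 1b. None of these is assigned to the comparison of uptake between a block and SOC.

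The denominators are not fixed in advance. Section 6.6.2 (Implementation) expects each block to last about three to four weeks and gives no length for the SOC period. Only men who were offered VMMC count, and section 6.2 (Study setting) says that under SOC "uncircumcised men with STIs are supposed to be offered VMMC at the STI clinic by clinicians however this is not reinforced". No uptake rate is assumed for either period: "Data on the incidence of VMMC among men with STIs is unavailable".

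**The concern.** Read conventionally, Student's t-test estimates one variance from both groups together. For a 0/1 outcome the variance is p(1−p). At low uptake, a block that works therefore has a larger variance than SOC. With equal group sizes, pooling does no harm. With unequal sizes, the pooled variance leans towards the larger group, and the standard error of the difference is wrong in a predictable direction.

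What is at stake is the interval around the main effectiveness result. A programme deciding whether to adopt RITE would look at the size of the uptake difference and its uncertainty, not only at whether p is below 0.05. The interval error appears under the kind of effect the study hopes to find.

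**Working it through.** **1. The plan's own figures.** Section 6.3 starts from 27 men a day, 28% of them circumcised: 27 × (1 − 0.28) = 19.4, taken as 19 a day. Then 19 × 20 = 380 a month and 380 × 6 = 2280, which reproduces the stated minimum. No power, target difference or uptake rate accompanies it.

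**2. Group sizes.** At 5 clinic days a week (my assumption), 19 × 5 = 95 men a week. Three weeks give 285 and four give 380. This treats every uncircumcised attender as offered VMMC. Section 6.2 quotes about 80 patients a day and section 6.3 about 60. Scaling both groups alike leaves their ratio unchanged, and the width error depends essentially on that ratio.

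**3. Uptake rates.** All are assumed: 2% or 5% under SOC, 10% or 20% in a block.

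**4. Formulas.** Let v = p(1−p), with subscript 0 for SOC and 1 for the block.
- Student: SE² = [(n0·v0 + n1·v1)/(n0 + n1 − 2)] × (1/n0 + 1/n1)
- Correct: SE² = v0/n0 + v1/n1

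If n0 = n1, the two agree apart from the degrees-of-freedom term. If v0 = v1, they agree for any sizes.

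**5. One case in full: SOC 380, block 285, uptake 5% v 20%.** v0 = 0.0475 and v1 = 0.16.
- Student: (380 × 0.0475 + 285 × 0.16)/663 = 63.65/663 = 0.0960. Multiplied by (1/380 + 1/285) = 0.00614, this gives SE = 0.0243 and half-width 1.96 × SE = 4.76 points.
- Correct: 0.0475/380 + 0.16/285 = 0.000686, so SE = 0.0262 and half-width 5.14 points.
- Ratio 0.927: about 7% too narrow.

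With the sizes reversed (SOC 285, block 380), the half-widths are 5.14 (Student) and 4.75 (correct): about 8% too wide.

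**6. Exact coverage of the nominal 95% Student interval.** Every pair of binomial outcomes was enumerated, two-sided, with men as independent units.

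| SOC n v block n | 5% v 10% | 2% v 10% | 5% v 20% | 2% v 20% |
|---|---|---|---|---|
| 380 v 380 | 95.0% | 94.8% | 95.0% | 94.9% |
| 285 v 380 | 95.7% | 97.0% | 96.6% | 97.1% |
| 380 v 285 | 94.1% | 91.6% | 93.0% | 91.8% |
| 190 v 380 | 97.1% | 98.4% | 98.1% | 98.9% |
| 380 v 190 | 92.4% | 88.3% | 89.6% | 86.5% |
| 95 v 380 | 98.1% | 99.5% | 99.4% | 99.8% |

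Only the first three rows use sizes implied by the plan. The rows with 190 or 95 men are assumptions.

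**7. Cases where nothing goes wrong.** With equal uptake of 2% or 5% in both groups, coverage is 95.0% to 96.3% at every size pair. At 30% v 70%, where the variances are equal, 380 v 285 gives 95.0%.

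**8. The test.** Rejection rates of Student's t and the uncorrected chi-squared test agree to within 0.1 percentage point in every scenario. Type I error at equal uptake is 3.7% to 5.0%.

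**9. The alternative interval.** The Newcombe interval covers about 95% to 97% throughout.

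**The case against.** The strongest reply is that the planned test reaches the right decision. Its p-value is practically the chi-squared one, so changing the test alone alters almost nothing. That stands.

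The reply continues that the plan's own group sizes put coverage at 92% to 97%, a modest error, and that the larger figures need imbalances and uptake rates that appear nowhere in the documents. That also stands. Moreover, the remark in section 6.2 about offers under SOC points towards fewer SOC men, which makes the interval too wide and so conservative. The too-narrow direction rests only on the unstated SOC length.

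Finally, the plan does not mention pooled variance, and it does not say which quantity the 95% interval is for. Both are the usual reading of the words. If an unequal-variance (Welch) version was meant, the section should say so. Welch covers 94.9% to 95.1% at 285 v 380, but falls to 85.5% at 380 v 95 with 2% uptake in both groups.

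A reader might infer three stronger claims, and none is supported:
- **The interval is wrong whenever the denominators differ.** It is not: with equal uptake or equal variances, coverage stays at about 95% to 96%.
- **The significance verdict is unsafe.** Step 8 of the working shows otherwise.
- **The normal approximation breaks down when SOC yields only about two events.** At 95 v 380 with 2% in both groups (95 × 0.02 = 1.9 expected SOC events), coverage is 96.3% and type I error 3.7%.

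**Conclusion.** The point holds as a fault in stated precision. If both the denominators and p(1−p) differ, the planned interval has the wrong width, and nothing in the plan prevents that combination.

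Within 285 to 380 men per group, the effect is modest: about 92% to 97% coverage against a nominal 95%. At 2:1 or greater imbalance it becomes material. At 2% v 20%, the average half-width around the 18-point difference is 4.5 points by Student against 5.9 by Newcombe at 380 v 190, and 8.2 against 5.5 at 95 v 380. The unstated SOC length and the offered-only denominator leave such imbalance possible, but the documents do not predict it, so those figures should not be read as the expected performance.

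The conclusion rests on pooled variance as the meaning of Student's test, two-sided 95% intervals, independent men, and uptake rates that are all assumed. It concerns only the error model for the difference. Confounding between calendar periods and the choice of denominator are separate matters.

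**What to change.** Under Data Analysis, Objective 1, replace the Student's t-test sentence. For each block against SOC, report the difference in uptake proportions with a Newcombe or Miettinen-Nurminen 95% interval. Test it with a chi-squared test, or Fisher's exact test if any expected count is below 5. Delete the normality assumption for this comparison and name the uptake difference as the quantity the interval describes.

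The interval is the part that matters; the change of test brings the wording into line with a binary outcome. The cost is one sentence in the analysis section. It needs no new data and no change to conduct or sample size, and the Newcombe interval held its coverage at every combination of group sizes tried.

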Objective 1b: To assess factors affecting uptake of voluntary medical male circumcision among men attending Bwaila STI clinic in Lilongwe Malawi

We will collect data on demographic, sexual and HIV/ART will be collected from the Bwaila STI clinic electronic medical registry and exported to Microsoft excel spreadsheet. Data will be

exported on a weekly basis by a data assistant. We will use these covariates to assess factors affecting uptake of VMMC among men who will undergo VMMC.

Objective 2: To develop STI clinic setting-specific voluntary medical male circumcision educational material at Bwaila STI clinic in Lilongwe Malawi

To achieve this objective, firstly, we will collect data from the consultative meeting with key stakeholders outlined in the above sections as notes. The notes will be collected by the investigator and another note-taker. Data will be analyzed in real-time. The suggested content and delivery methods will be identified. Secondly, we will conduct a pilot of the intensified health education material and methods on men accessing care at Bwaila STI and collect more notes on possible ways to refine intensified health education. Any necessary refinements will be done and the intensified health education material and methods will be endorsed.

Objective 3: To assess the acceptability, appropriateness and feasibility of the RITE intervention among men and healthcare workers at Bwaila STI clinic in Lilongwe, Malawi.

Acceptability will be defined as the perception among men and HCWs that the RITE intervention is agreeable, palatable and satisfactory [36]. Appropriateness will be the perceived fit of the RITE intervention to address the problem of low uptake of VMMC among men and HCWs [36]. Feasibility will be the extent to which the RITE intervention will be successfully carried out at Bwaila STI clinic [36]. Acceptability, appropriateness and feasibility will be measured quantitatively using surveys and qualitatively using in-depth interviews (IDIs) and focus group discussions (FGDs). Acceptability and appropriateness will be measured before (at

baseline) and during implementation of our intervention for each implementation block.

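### Objective 1b lets univariable P<0.05 decide which covariates enter the factor model, and the expert-knowledge route that could offset this is not prespecified

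*Combined protocol and SAP*

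**What the plan says.** The analysis of Objective 1b is set out in the data analysis text under section 6.3 (Sample Size Calculation and Justification). The model type is given first: "We will assess factors affecting uptake of VMMC using logistic regression modeling". A screening step follows: "We will use univariate models to assess association". The entry rule is then: "Covariates with $P<0.05$ and those based on expert knowledge of this topic will be fit into multivariate logistic regression models to control for confounders". There are therefore two routes into the model, both contained in the words "Covariates with $P<0.05$ and those based on expert knowledge": univariable significance, or expert judgement.

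The candidate pool is described by class. Under Objective 1b, section 6.2 (Data Collection) says: "We will collect data on demographic, sexual and HIV/ART will be collected from the Bwaila STI clinic electronic medical registry". The opening of that section names age, marital status, education and socioeconomic status, and says that sexual history, HIV status and ART status may be added. Nowhere is it stated which covariates count as expert-chosen, who chooses them, when, or whether they stay in whatever their P value. Implementation block and symptomatic or partner status are not named for this model.

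On size, section 6.3 says: "we expect that a minimum of 2280 uncircumcised men will be exposed to our intervention and observed for VMMC uptake". It gives no uptake rate: "Data on the incidence of VMMC among men with STIs is unavailable".

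**The concern.** A univariable P value measures crude association with uptake. Whether a variable confounds another depends on its relation to both the factor and the outcome, and a crude P value does not show this. The screen fails most where adjustment is most needed: if two related characteristics act on uptake so that one hides the other, the hidden one looks null alone and is not admitted on its P value.

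Two further effects follow. Weak factors that do pass tend to be those whose estimates came out high by chance, so the reported odds ratios may be inflated. The final P values and intervals also take no account of the selection step.

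At stake is the list of factors reported as affecting uptake. It may omit real ones, and those it includes may be incompletely adjusted. Section 6.5 (Limitations) names differences in the men enrolled per block and seasonality as threats. For the uptake proportion, this logistic model is the only analysis described as controlling for confounders.

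**Working it through.** **1. The plan's own number.** 27 men per day x (1 - 0.28) = 19.4, taken as 19. The plan's 380 per month implies 20 clinic days (19 x 20 = 380). Over 6 months, 380 x 6 = 2,280, so the stated minimum reproduces. If the standard-of-care period and the four blocks each last 3 weeks, the short end of the 3-4 weeks in section 6.6.2, the total is 19 x 15 x 5 = 1,425. At 4 weeks it is 19 x 20 x 5 = 1,900. Equal length for the standard-of-care period is an assumption.

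**2. The screen with no masking.** Take one true binary predictor with 50% prevalence, reference uptake 10%, odds ratio 1.5, N = 2,280 and two-sided alpha 0.05.
- Exposed uptake: odds 0.1111 x 1.5 = 0.1667, so p = 0.1429.
- Null standard error: sqrt(2 x 0.1214 x 0.8786 / 1,140) = 0.01368.
- Alternative standard error: sqrt((0.0900 + 0.1224) / 1,140) = 0.01365.
- z = (0.0429 - 1.96 x 0.01368) / 0.01365 = 1.18, so the factor passes about 88% of the time.

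Over reference uptake 5% to 20% and prevalence 20% or 50%, the pass rate at 2,280 men is 24% to 74% for odds ratio 1.3, and 50% to 98% for odds ratio 1.5. All of these rates are assumed, because the documents give none.

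**3. The screen with masking.** Assume two binary covariates at 50% prevalence, a factor with true odds ratio 1.65, a confounder with odds ratio 2 and a latent normal correlation of -0.6.
- Confounder prevalence among men with the factor: 0.5 + arcsin(-0.6)/pi = 0.295. Without the factor: 0.705.
- Approximate confounding ratio for an uncommon outcome: (1 + 0.295) / (1 + 0.705) = 0.76.
- Expected crude odds ratio: 0.76 x 1.65 = 1.25.

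Simulation at N = 1,425 and uptake about 8-9% agrees: crude odds ratio 1.26 and adjusted 1.67.

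| Latent correlation | Passes univariable P<0.05 | Significant when entered regardless |
|---|---|---|
| -0.6 | about 23% | about 68% |
| -0.3 | about 50% | about 75% |
| 0 | no gap | no gap |

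**4. A second assumed setting at 2,280 men.** Odds ratios 1.6 and 0.4, correlation 0.6, 1,000 runs, simulation error about 3 points. At uptake about 9%, the masked factor passes in 10% of runs, against 84% significant when both covariates are entered. At about 4.5% uptake it is 8% against 55%. With zero correlation the figures are 89% against 89%, and 64% against 64%.

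**5. Inflation after selection** (N = 1,425, uptake about 11-12%, 600 runs). Among runs where the masked factor passed the screen, the median adjusted odds ratio was 1.98 against a true 1.65. With no masking, a weak factor (true 1.35) passed in 37% of runs, with a median estimate of 1.60; interval coverage in that case stayed close to nominal.

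**6. Events for a fixed list.** With 1,425 men: 0.05 x 1,425 = 71; 0.07 x 1,425 = 100; 0.10 x 1,425 = 142. With 1,900 men at 10%: 190. For about 15 terms (block alone takes four), that is 4.7, 6.7, 9.5 and 12.7 events per term.

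**The case against.** The strongest reply is that P<0.05 is not the only way in. The sentence that sets the threshold also admits covariates on expert knowledge, so a masked factor is lost only if the experts also leave it out. This stands. A reader might infer that every masked variable is discarded; the text does not support that.

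A reader might also infer that experts will add variables after seeing the results. The plan states no sequence. What can be said is that neither the list nor its timing is fixed.

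The simulated rates describe a screen-only rule, so they are not failure rates of this plan. They also rest on a strong assumed imbalance, with the confounder present in about 30% of one factor group and 70% of the other. Nothing in the documents shows such imbalance, and without correlation there is no loss from masking. This stands too.

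The candidate variables are partly named in section 6.2 (Data Collection), so the pool is not wholly open. But naming what will be collected does not commit the analyst to what will be adjusted for.

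Finally, a full fixed list may be too long for the events available. That is a fair limit on the remedy, but it is no argument for choosing covariates by P value.

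**Conclusion.** The concern holds in a limited form. The P<0.05 route is a poor selector for a model meant to control confounding. The route that could compensate for it is not specified, so its protection cannot be verified. Under the step 3 assumptions, the difference between screening and entering regardless is 68% - 23% = 45 points at correlation -0.6, 75% - 50% = 25 points at -0.3, and nil at zero. Correlation, effect sizes and uptake are all assumed. Estimates and intervals for weak factors may be optimistic after selection; the documents do not allow the statement that they will be.

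The effect is confined to sub-objective 1b. A reader might extend it to the main uptake result, but Objective 1 compares each block with standard of care by an unadjusted test that uses no covariate model, so this selection rule does not touch it. This is an inexpensive improvement to a secondary analysis.

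**What to change.** Remove P<0.05 as an entry criterion. Before uptake data are seen, fix one covariate list for the Objective 1b model: age, marital status, education, socioeconomic status, HIV/ART status, symptomatic or partner status, and study block. Keep all terms whatever their P value, report every coefficient with its interval, and present the univariable results as description only.

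The cost is SAP wording; the covariates are routine clinic data or follow from the study period. The statistical price is slightly wider intervals from keeping weak terms. At 10% uptake, about 142 to 190 events give roughly 9 to 13 per term for 15 terms. If uptake is nearer 5-7%, about 71 to 100 events at 1,425 men do not comfortably support the full list. The SAP should therefore name in advance a shorter list or a penalised fit for that case, and the event count that triggers it.

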This will be full roll-out of our intervention. The intervention will have four implementation blocks (Appendix 1) that will be different combinations of the intervention components in an incremental manner. There will be one week of no intervention between interventions as a wash-out period. The implementation will be as follows: First we will observe the SOC VMMC referral process. In **block one**, we will introduce IHE which will then be maintained throughout the implementation period. Clinic escorts combined with IHE in **block two**. **Block three**, IHE, clinic escorts and SMS tracing will be combined. In **block four**, all intervention components will be combined including transport reimbursement to form the full intervention. Supportive supervision and constructive feedback will be maintained throughout the implementation period. Based on the sample sizes detailed below, we anticipate that each intervention block will last about 3-4 weeks.

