Feasibility will be measured during implementation for each implementation block because it cannot be measured before exposure to the intervention [36]. A vignette (embedded in the data tools) on the RITE intervention will be read out to respondents to describe the intervention. Data on acceptability, appropriateness and feasibility will be collected using the following methods:

Surveys: For acceptability, we will use the acceptability of intervention measure (AIM), a tool designed by Weiner et al [37], to collect quantitative data for acceptability. The AIM uses Likert scales of four constructs which assess if an intervention is appealing, likeable, welcome and approved. For appropriateness, we will use the intervention appropriateness measure (IAM) to collect quantitative data for appropriateness [37]. The IAM uses a Likert scales of constructs which assess if an intervention is fitting, suitable, applicable, and a good match. For feasibility, we will used the feasibility of intervention measure (FIM) for feasibility Surveys [37]. The FIM uses a Likert scales of constructs which assess if an intervention is implementable, possible, doable, and easy to use. These tools have been slightly modified to suit the study setting.

Acceptability and appropriateness will be conducted at baseline and for each implementation block except for feasibility which cannot be assessed before exposure to the intervention (Appendix 6 - 9). Surveys data will be collected on electronic tablets through open data kit (ODK). Data clerks will administer surveys on an electronic tablet for the men while HCWs will self-administer the surveys. Each survey will to last approximately 10 - 20 minutes. Survey data will be downloaded from the tablets to a Microsoft Access password-locked database. IDIs and FGDs will complement the surveys.

In-depth interviews: IDIs will be conducted with HCWs from Bwaila STI clinic only. IDIs will

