calculated as a median score and percentages for each of the survey questions. The results will be compared between SOC and each implementation block using Wilcoxon sign-ranked test, analysis of variance (ANOVA) and test of proportions as required. We propose to use structural equation modelling to assess predictors of acceptability, appropriateness and feasibility. The latent variables will be acceptability, appropriateness and feasibility. We assume that the constructs measuring each of these latent variables are correlated, we will conduct principal component analysis and calculate factor loadings and error variance to estimate the true effect of the constructs. We also assume that the latent variables will be correlated. Therefore, we will conduct confirmatory factor analysis to assess how the latent variables will affect the impact of our intervention on uptake of VMMC.

Qualitative data will be analyzed using a thematic approach (thematic framing and coding, indexing, and charting). We will conduct data analysis concurrent with interviews to identify salient themes and areas that may require further exploration in the subsequent interviews. Salient themes will be deduced from codes identified from the IDIs and FGDs.

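### Acceptability and appropriateness are compared with standard of care question by question, with no scale score, lead contrast or multiplicity rule, which inflates false differences and loses precision

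*Combined protocol and SAP*

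**What the plan says.** The analysis text is in section 6.3 (Sample Size Calculation and Justification), under Data Analysis, Objective 3. The three survey outcomes are to be "calculated as a median score and percentages for each of the survey questions". It continues: "The results will be compared between SOC and each implementation block using Wilcoxon sign-ranked test, analysis of variance (ANOVA) and test of proportions as required".

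Section 6.2 (Data Collection), under Surveys, describes the instruments. For acceptability: "The AIM uses Likert scales of four constructs which assess if an intervention is appealing, likeable, welcome and approved". For appropriateness: "The IAM uses a Likert scales of constructs which assess if an intervention is fitting, suitable, applicable, and a good match". On timing: "Acceptability and appropriateness will be conducted at baseline and for each implementation block except for feasibility which cannot be assessed before exposure to the intervention". Feasibility therefore has no baseline value to compare with. The same section says that the tools were slightly modified for the setting.

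Section 6.6.2 (Implementation) sets four blocks after the SOC period.

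The Objective 3 text also assumes correlated items, treats the three outcomes as latent variables, and plans structural equation modelling, principal components and confirmatory factor analysis. These serve two purposes: finding predictors of the outcomes, and relating the outcomes to uptake. They are not the stated method for comparing SOC with each block.

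**The concern.** AIM and IAM each use several items to measure one idea. Objective 3 asks whether the intervention is acceptable and appropriate, not whether one item out of eight moved in one block out of four. On its natural reading the plan tests each question separately in each block, and nothing says which result carries the conclusion.

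Two things follow. Some item in some block is likely to differ from SOC by chance, and a claim could rest on it. In addition, each test uses one item's information when four items on the same idea are available from the same men. The results matter because acceptability, appropriateness and feasibility make up the implementation science aim in section 6.1 (Study design) and one of the three proposed publications.

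**Working it through.** **Inputs from the documents.** Four AIM items and four IAM items (the IAM count is taken from the list in section 6.2; the survey forms are not shown). Four blocks. Surveys per block: "we calculated that 67 surveys are required for each intervention component to achieve 95% confidence level with 5% margin of error".

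**Assumptions.**
- Two-sided alpha of 0.05. No level is stated for Objective 3; the Objective 1 comparison uses 0.05 ("significance level and 95% confidence interval, assuming normal distribution").
- 67 men at baseline as well as in each block, since the plan gives 67 per intervention component only.
- Item correlation varied over a range, since the plan assumes correlation but gives no value.

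**The plan's own figure.** n0 = 1.96² × 0.25 / 0.05² = 384.1. With a population of 80, n = 384.1 / (1 + 383.1/80) = 66.4, rounded up to 67. It reproduces. This is a margin-of-error calculation and does not address comparisons between blocks.

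**Number of tests.** 8 items × 4 blocks = 32 for men. Expected false positives with no true difference: 32 × 0.05 = 1.6, whatever the correlation. Testing both scores and percentages, or adding healthcare workers, would increase the count.

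**Chance of at least one false difference.** If all 32 tests were independent, 1 − 0.95^32 = 0.81. They are not: every block shares the baseline group, and items correlate. Simulation with a shared baseline (100,000 runs per setting) gives:

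| Correlation within / between scales | 32 item tests | 8 scale tests |
|---|---|---|
| 0 / 0 | 0.74 | 0.29 |
| 0.3 / 0.2 | 0.71 | 0.27 |
| 0.4 / 0.3 | 0.675 | 0.26 |
| 0.5 / 0.3 | 0.65 | 0.27 |
| 0.5 / 0.4 | 0.64 | 0.26 |
| 0.7 / 0.5 | 0.55 | 0.26 |
| 0.8 / 0.6 | 0.49 | 0.25 |
| 0.9 / 0.8 | 0.38 | 0.22 |

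A check with five-point responses, 67 per group and rank-sum tests (the men differ between blocks), 1,500 runs per setting, gave 0.70 (0.3/0.2), 0.65 (0.5/0.3 and 0.5/0.4), 0.59 (0.7/0.5) and 0.51 (0.8/0.6) for the item tests, and 0.25 to 0.28 for the scale tests.

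**If one omnibus test per item is used.** Eight tests: at most 1 − 0.95^8 = 0.337 if independent.

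**After scoring the scales.** 2 scales × 4 blocks = 8 tests leave about 0.21 to 0.29 across the runs. Comparing one block on both scales leaves 0.07 to 0.10. A single named contrast on one scale leaves 0.05.

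**Precision.** For a shift common to all items with observed correlation r, the SD of a four-item mean is √((1+3r)/4) item SDs, so the standardised difference grows by √(4/(1+3r)). With 67 per group, a single item has a detectable difference at 80% power of (1.96 + 0.84) × √(2/67) = 0.48 item SD, and power of 0.64 for a shift of 0.4 item SD. For the four-item mean:

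| r | Gain factor | Sample needed v one item | Detectable difference (item SD) | Power for 0.4 item SD |
|---|---|---|---|---|
| 0.3 | 1.45 | 47.5% | 0.33 | 0.92 |
| 0.5 | 1.26 | 62.5% | 0.38 | 0.83 |
| 0.7 | 1.14 | 77.5% | 0.43 | 0.75 |
| 0.8 | 1.08 | 85% | 0.45 | 0.71 |

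**The case against.** The strongest reply is that the wording allows other readings. The sentence could mean one median score per outcome, with percentages for each question. The tests are to be applied as required, and ANOVA could compare all groups at once, giving 8 tests and not 32. No significance level is set for Objective 3. The surveys are sized by margin of error, and interviews and focus groups complement them. All of this stands as a limit on the size of the problem. None of it supplies a scale score, a lead contrast or a multiplicity rule, and even the omnibus reading allows up to 34%.

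Four stronger conclusions are tempting and are not supported:

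- A reader might infer that about two-thirds of such studies would show a false difference. That holds only for 32 pairwise tests at 0.05 and an observed item correlation of about 0.4 to 0.5, a value the documents do not give.
- A reader might infer that the plan ignores the scale structure. It does not: it plans latent-variable models, but for other questions.
- A reader might infer that coarse item medians would hide real shifts from the tests. The named tests use ranks, means or proportions, so coarseness affects only the descriptive summary.
- A reader might infer that scale scoring alone cures the error rate. Eight scale tests still leave about 21% to 29%.

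**Conclusion.** The point holds with these limits. On the natural reading, the comparison with SOC is made per question, uncontrolled, with no lead result. If every item is tested pairwise in every block, the chance of at least one false difference among men is roughly 40% to 75%; even the lowest tabulated value, 0.38, is more than seven times 0.05. These figures rest on an assumed alpha, an assumed 67 men at baseline, pairwise testing and an unknown item correlation.

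The loss of precision is real but modest if items correlate highly, and it applies to shifts shared by all items. The gain from scale scores needs no extra data.

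This affects a secondary, implementation objective. It does not touch the uptake comparison. The change is worth making because it is nearly free and settles which result answers the objective.

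**What to change.** Amend the Objective 3 text under Data Analysis in section 6.3 as follows:

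1. Score each instrument (AIM, IAM, FIM) as the mean of its items, once the planned factor analysis has confirmed that the modified items form one scale. State in advance what will be done if they do not.
2. Base comparisons with SOC on the AIM and IAM scores, each reported as a difference with a 95% confidence interval. FIM has no baseline and is described by block.
3. Name one lead contrast before the data are seen, for example full RITE against SOC on AIM. State the significance level and label the remaining contrasts as supportive.
4. Report item medians and percentages descriptively, without tests.

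If the existing sentence was meant to describe one overall score per outcome, the same edit makes that clear.

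The cost is a few sentences of plan wording. No new data, visits or participants are needed. The only loss is that item-level differences become descriptive.
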